#### 7. Statistical Analysis.

**Phase 3 Data Analysis**. The objectives of phase 3 are to: 1) maintain data files; 2) evaluate study outcomes; and 3) disseminate study results and project materials.

**Data management** Procedures for data management and monitoring will be initiated during the start-up phase. The project coordinator will coordinate the organization and processing of forms, and schedule and implement checks of data quality and completeness. Data from the ACASI files will be saved in the database. Data will be backed up on a regular basis to prevent loss of data. Data will be transferred electronically from the sites to a secure password protected network drives where it will be checked and downloaded. A data-checking plan based on each questionnaire will be used to look for suspicious entries. Data monitoring will be merged as necessary to answer the research questions. [name] will oversee the final quality assurance/quality control data reviews. She will design and conduct the statistical analyses; assist as needed with designing research forms and data entry; and collaborate with the investigators on analysis and interpretation. We have successfully used these procedures in our research projects.

**Sample size and Power Calculation.** For longitudinal analyses of cognitive functioning and biological measures (Aims 1 and 2), our sample size provides adequate power (80%) to detect effect sizes of 0.37 or larger at alpha=0.05. Our ongoing study (Caregiver Stress study) showed that between-group effect sizes related to exercise vs. AC groups are on the order of 0.5 to 0.8 for physiological, physical and psychological functions.

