AIM 1. Neurocognitive Improvement: We expect the primary cognitive improvements to be found in executive skill, episodic memory, and processing speed (as measured by CANTAB) since these skills are most susceptible to the effects of exercise. As recommended by Grant and Marcotte, demographically adjusted scores will be used to test for intervention effects between the treatment and attention control conditions over the study time period. To adjust for the effects of practice from repeated testing, we develop z-scores for each of the neuropsychological assessment tests using the regression-based method. Specifically, we first use multiple regression from control participants' test scores to derive the norms for change across visit times. Then we calculate the z-score by adjusting the raw test score with the expected normal follow-up score based on the subject's baseline characteristics using the multiple regression model. This method accounts not only for the effects of practice but also test-retest reliability (e.g., regression to the mean, ceiling and floor effects) and is the method suggested for use with clinical samples. The z-scores will be used as the outcome measures in the following statistical analyses. We will then use the confidence-interval-based method to classify whether a subject has shown improved cognitive functioning when comparing to the norms for change. Specifically, we will define "no change" on each cognitive test using a 90% confidence interval (CI) based on the norms generated from the control subjects' data. Then, participants who score above the upper bound of the 90% CI, i.e. in the top 5% of the normal distribution, will be defined as "improved", while those within the 90% CI defined as "no change" and those below the lower bound of the CI defined as "decliners". Modeling and Hypothesis testing. Repeated measures analysis will be performed to model the z-scores of the NP tests, the classified improvement status and other outcome measures longitudinally to test whether there are differences between the two intervention groups in terms of executive skill, episodic memory and information

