processing speed at T1 and T3 assessments. Specifically, multilevel models including linear mixed models Version 02.15.2018 Page 18 of 30 (LMM: for continuous outcomes) and generalized linear mixed models (GLMM: for categorical outcomes) will be implemented using SAS (version 9.3; SAS Institute, Cary, NC) where each subject is treated as an experimental unit in the mixed model. An unstructured variance–covariance form will be assumed in repeated measurements within a subject, which provides the most flexible modeling of the covariance structure. Predictors in the models will include 1) visit time 2) intervention group, 3) interaction term between visit time and intervention group and 4) potential confounding factors such as nadir CD4 count, the CPE score (CNS penetration effectiveness of the antiretroviral regimen), ART adherence, time since diagnosis, estimated premorbid IQ, and HAND diagnosis. The fitted mixed model will provide model-based estimates and tests for the outcome measures for the two intervention groups at each time point of the study. Hypotheses tests based on specific contrasts in the mixed model and the interaction term between visit time and intervention group will be performed to test the hypotheses that subjects in the Let's Move program demonstrated improved cognitive functioning as compared to Let's Flex control group.

**AIM 2.** Repeated measures analysis using multilevel models will be performed to test whether there are differences between the two intervention groups in terms of the inflammatory biomarkers, endothelial vascular function and neuronal growth biomarker at T1 and T3 assessments. Prior to fitting the multilevel models, the distributions of the biomarkers will be checked and appropriate transformations will be performed for skewed biomarkers. Similar strategies as in Aim 1 will be used to construct the multilevel models and to perform model-based tests to evaluate the hypotheses in Aim 2.

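### Aim 1 scores both arms against change norms apparently fitted in the Let's Flex arm, which distorts improved/decliner status, and leaves open which test decides efficacy

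*Combined protocol and SAP*

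**What the plan says.** Section 7 (Statistical Analysis, Aim 1) builds the cognitive outcome in two steps.

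- **Norms.** For norms of change across visits, "we first use multiple regression from control participants" is the stated source. Each follow-up score becomes a z-score against the value expected from that participant's baseline characteristics. Those characteristics are neither listed nor counted.
- **Status.** No change is defined "using a 90% confidence interval (CI) based on the norms generated from the control subjects". Scores above the band (nominally the top 5%) count as improved, and scores below it as decline.

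Both products are outcomes. The plan says "The z-scores will be used as the outcome measures in the following statistical analyses", and the repeated measures analysis is to "model the z-scores of the NP tests, the classified improvement status and other outcome measures longitudinally". It adds that "generalized linear mixed models (GLMM: for categorical outcomes) will be implemented using SAS", but not how three classes enter such a model.

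On testing, the fitted model is to give "model-based estimates and tests for the outcome measures for the two intervention groups at each time point of the study", and hypothesis tests based on "specific contrasts in the mixed model and the interaction term between visit time and intervention group will be performed". The contrasts are not defined, and none of these tests is named as the one that decides efficacy.

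**The concern.** Let's Flex is the only control group the document describes, and no external norm sample is named. If Flex supplies the norms, each Flex participant is scored by a regression that was fitted to that participant's own data, while each Let's Move participant is scored by a regression fitted to other people. Least-squares residuals are too small in the fitting sample and too large outside it. The two arms would then differ in spread, and so in the share beyond any fixed cut, even if exercise did nothing.

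The second issue is separate. A z-score defined against an expected follow-up score exists only after baseline. With no baseline row in the model, the visit-by-group interaction asks whether the arm difference changes between follow-ups, not whether there is one. A benefit that appears by T1 and holds to T3 produces no interaction.

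**Working it through.** **Inputs.** Taken from the document: cut at the top 5%, two-sided alpha 0.05, effect size 0.37, T1 and T3 as the analysed visits, 20% attrition. Arm sizes (Flex/Move): 68/132 from the Abstract and Objectives; 54/106 after 20% attrition (0.8 × 68 = 54.4; 0.8 × 132 = 105.6); 43/85 as a 2:1 split of 128. Assumed: the number of norm predictors p, normal errors, complete data, within-subject residual correlation 0.5.

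**The plan's own figure.** With known norms, P(z > 1.645) = 5%, as stated.

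**Leading-order check, n = 54 controls.** With z = residual / residual SD from the control fit:

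- in-sample variance (Flex) ≈ 1 − (p+1)/n
- out-of-sample variance (Move) ≈ 1 + (p+1)/n
- tail share = P(Z > 1.645 / SD)

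| p | (p+1)/n | Flex SD | Flex tail | Move SD | Move tail |
|---|---|---|---|---|---|
| 1 | 2/54 = 0.037 | 0.981 | 4.7% | 1.018 | 5.3% |
| 5 | 6/54 = 0.111 | 0.943 | 4.1% | 1.054 | 5.9% |
| 8 | 9/54 = 0.167 | 0.913 | 3.6% | 1.080 | 6.4% |

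The Move figures are slightly low because the formula ignores error in the residual SD and higher-order terms.

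**Simulation with no true effect, 54/106.** Improved, Flex vs Move: about 4.7 vs 5.6% (p = 1), 4.4 vs 6.0% (p = 3), 4.0 vs 6.4% (p = 5), 3.6 vs 7.0% (p = 8). Decliner rates match to about 0.1 point. The mean z difference lies between −0.005 and +0.002 in every cell.

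**Type I error by outcome (nominal 5%), three 2:1 sizes.**

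- Continuous z, no covariates: 5.1-6.5% for p = 2 to 8.
- Continuous z with the norm covariates also in the group model: 4.6-5.6%.
- Three classes scored −1/0/1 and averaged, pooled variance: 5.0-6.8%. An unequal-variance version gives 5.6-7.1% for p = 1-3 and up to 11.1% at p = 8.
- Improved versus not, robust logit test: 4.4-6.7% for p = 1-3, 7.9-8.8% for p = 5, 13.9-16.9% for p = 8, against 3.1-4.4% with known norms. An independent run with a simpler one-visit test at 54/106 and p = 5 gave 5.88 + 1.27 = 7.15%, hence about 7-9% overall. In the two-visit runs, 95% or more of the false positives at p = 5 favoured Let's Move.
- Section 5 prints Flex 107 and Move 53. At those sizes the robust logit test rejects 4.0-5.6% for p = 1-5 and 8.6% for p = 8.

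**Interaction versus arm contrast.** Let the true benefit on z be d at T1 and d at T3. The interaction estimates d − d = 0, while the averaged arm contrast estimates (d + d)/2 = d. Take a steady 0.37 SD, the size for which the plan says "our sample size provides adequate power (80%) to detect effect sizes of 0.37 or larger at alpha=0.05" (assumed to be in SD of the score), with baseline-follow-up correlation 0.5-0.8. The interaction on z rejects in 6.5-9.0% of trials, against 5.5-6.7% with no effect. The arm contrast averaged over T1 and T3 rejects in 71-100%. If a baseline row could be modelled, the arm-by-visit test would reject in 48-99%, but the z-score is not defined at baseline.

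**The case against.** **The norm sample may not be Let's Flex.** The plan never says outright that it is, and the reference list includes a paper on normative data for neuropsychological change. With external norms both arms are scored out-of-sample and the artefact goes. This stands as a limit on the inference. Even so, the text derives the norms from control data, and Aim 1 calls Let's Flex the control group. Any other norm sample would have to be named.

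**The clear inflation needs assumptions.** It takes about five or more norm predictors and a binary test that the plan does not specify. With one to three predictors the effect on that test is small. This also stands. A random-intercept logistic model gave higher rejection (11-15% at p = 5), but it held only visit and arm, not the planned interaction, site and covariates, and it rejected 5.7-6.1% even with known norms. It should not be read as the error rate of the planned analysis.

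**The z-scores can be kept.** Section 7 already adjusts for baseline factors. Carrying the norm covariates into the group model brings z back to about 5%, so a reader who concludes that the cited scoring method must be abandoned goes too far.

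**The interaction need not decide.** A reader might infer that the trial has almost no power. The documents do not support that: the Objectives hypothesise higher scores in Let's Move at follow-up, and Aim 1 asks about arm differences at T1 and T3. Both describe arm contrasts. What remains is that the interaction is listed beside them and nothing ranks the tests.

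**Conclusion.** The concern holds in a limited form. If the norms come from Let's Flex and errors are symmetric, Let's Move will show more improvers and about equally more decliners with no true effect. At 54/106 the gap in each tail is about 1 point with one predictor (5.6 − 4.7), 2.4 with five (6.4 − 4.0) and 3.4 with eight (7.0 − 3.6). Strong ceiling or floor effects could make the tails unequal.

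It would be wrong to read this as a biased treatment effect: the mean z difference is unaffected, and continuous z is only mildly disturbed. The material risk is a one-sided artefact if status is collapsed to improved versus not with a rich norm regression, because the matching excess of decliners then drops out of sight. The plan leaves both the collapse and the predictor count open.

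The undesignated efficacy test is a separate gap that does not depend on who the controls are. The visit-by-group interaction on z-scores is unsuitable for that role. Both matters should be settled before analysis. Confidence is medium, since the size rests on an assumed predictor count.

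**What to change.** 1. Designate the arm contrast on the continuous outcome, at T1 and T3 or averaged over visits, as the efficacy test. Use the visit-by-group interaction only to describe change in effect over time.
2. Choose one of two routes for the continuous outcome. Either keep the z-scores, name the norm sample, list the norm predictors in advance and carry those covariates into the mixed model; or fit a one-stage mixed model to follow-up scores in both arms with baseline score by visit, visit, arm, arm by visit, site and prespecified baseline covariates. Under randomisation, practice effects common to both arms cancel in the arm comparison. The one-stage model held 4.2-5.6% type I error.
3. Make change-norm status descriptive, report improved and decliner rates together, and score each control from a fit that leaves that control out. At 54/106 this brings the improved rates level (Flex vs Move 6.45 vs 6.33% at p = 5; 7.09 vs 7.00% at p = 8); with prediction limits as well, both arms return to about 5%.

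The cost is SAP wording and a little more code, with no new data. Status loses its role as a tested outcome, and the one-stage route departs from the cited scoring. The conflicting arm sizes in the Abstract, Objectives and section 5 are a separate matter and must be reconciled.

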# 4. Objectives

Our home-based aerobic exercise intervention, the '*Let's Move Program*' has been tested and is effective for lowering CVD risk in previous trials of older caregivers and adults with advanced CVD. The proposed efficacy trial, Fit BRAiN will recruit 200 PLWH and randomize them (2:1) to either the *Let's Move intervention* (n=132) or an attention control condition, *Let's Flex* (n=68), and follow them for an additional 3 assessments/time points (at 13-15 weeks post baseline, 28-30 weeks post baseline and again at 56-58 weeks post baseline). Participants will be  $\geq$  50 years of age, sedentary, demonstrate objectively measured CI, and stable on antiretroviral medications for at least 6 months. Motivational Interviewing (MI) will be used to promote exercise self-efficacy and optimize adherence to the intervention and flexibility and stretching to the attention control arm. The following are our aims:

AIM 1: To test, in a RCT, the efficacy of the *Let's Move Program* to improve cognitive functioning in this sample.

H0 1: Participants in the *Let's Move* intervention will have significantly higher scores than participants in the Let's Flex attention control group on measures of executive skill, episodic memory, and information processing speed at 3 assessments/time points (averaging a total of 56-58 weeks) post-baseline.

**AIM 2:** To test, in a RCT, the impact of the *Let's Move Program* on inflammatory markers, endothelial vascular function, and neuronal growth factor (BDNF) in this sample.

H0 2: Participants in the *Let's Move* intervention will demonstrate improved *inflammatory markers, neuronal growth factor, oxidative stress, thrombotic tendency, and endothelial vascular function* compared to the Let's Flex attention control group at 3 assessments/time points (averaging a total of 56-58 weeks) post-baseline.

**Secondary Aim:** To explore the potential mediation effects of inflammatory biomarkers, endothelial vascular function, and neuronal growth factor on the relationship between the *Let's Move Program* and the cognitive skills measured in Aim 1.

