NIH Toolbox	Computerized cognitive tests developed and distributed by the NIH. Tests include Pattern Comparison Processing Speed Test, Picture Vocabulary Test, Reading Recognition Test, Dimensional Change Card Sort Test, Flanker Inhibitory Control and Attention Test, Picture Sequence Memory Test, List Sorting Working Memory Test, and Oral Symbol Digit Test	

Blood collection procedures: After overnight fasting, all blood samples will be collected with an intravenous (IV) catheter will be placed into a forearm vein or hand. Blood samples will be collected by a research staff or laboratory assistant trained in blood drawing techniques after 30 minutes of rest between 8-11:30 am (to control for circadian variation) in EDTA or Heparin tubes and immediately placed on ice. Where indicated, blood will be spun at 3,000 rpm for 15 minutes at 4C. Plasma samples will be coded, labeled and will be aliquoted into pre-cooled siliconized polypropylene tubes and stored at -80C until assayed for relevant biomarkers. Processing and analyses of specimens will be performed according to manufacturer ELISA recommendations. Blood collection for the measures in Table 5 will occur at **Baseline, T1, T2 and T3 assessments.** When the study is completed, the blood sample will be destroyed.

Flow mediated Dilation (FMD): A forearm test will be conducted to measure endothelial function at **Baseline, T1, T2, and T3 assessments** after overnight fasting. Participants will have a blood pressure cuff placed around one of their arms. The blood pressure cuff will be inflated and deflated and a trained clinical staff will use an ultrasound device to take measurements of the blood flow in the participants arm.

Table 5. Biological Measures			
Measures	Description		
Inflammatory Biomarke	rs		
Soluble Cluster of Differentiation 14 (sCD14)	Marker of monocyte activation, is associated with neurocognitive impairment and HANDs and higher mortality in PLWH. 		
Interleukin 6 (IL-6)	IL-6 is a well-established pro-inflammatory cytokine known to contribute to the pathogenesis of insulin resistance that contributes to increased risk of CVD and CI through inflammation and promotion of endothelial vascular dysfunction. IL-6 has also been associated with both depression and fatigue in both medically ill and medically healthy individuals. 		

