Statistical Analyses. General Considerations in Statistical Analyses: Our initial data exploration will include: 1) determining the distributions of outcome measures and assessing whether data transformations are needed, 2) insuring that the underlying assumptions of statistical analyses are satisfied, 3) identifying potential co-linearity problems, and 4) identifying potential outliers that require further investigation. For categorical variables, we will check for sparse cells and regroup categories if necessary. In building statistical models, we will check linearity assumptions for continuous predictors and consider higher-order terms if needed. *Missing* Data. We will make every effort to minimize missing data by monitoring the degree of missing data regularly and implementing successful methods for obtaining follow-up data. When data cannot be collected, sensitivity analysis will be performed to evaluate the impact of missing data on results. We also plan to use restricted maximum likelihood (REML) method for estimating the longitudinal statistical models to minimize the impact of missing data. This will make it possible to retain cases with partial data while making less restrictive assumptions about missing data patterns. Controlling for Confounding. Our analyses will account for potential confounding factors such as medications, gender, BMI and other specific confounders for each aim. Adjustment for stratification variables. We plan to adjust for the stratification variable, i.e. study site, in the statistical analysis. This will correct for correlation between the treatment groups due to the balanced randomization within each site and consequently provide better statistical power in detecting differences between treatment groups. Adjustment for Multiple Measures and Comparisons. We will apply adjustments such as Bonferroni correction when appropriate to adjust for multiple comparisons. A combination of statistical software will be used for statistical analysis and data visualization, including SPSS (v.20), SAS (v. 9.3), and R (v. 3.0.1). All statistical tests will be two-sided and intent-to-treat procedures will be employed.

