**AIM 3.** To assess whether the association between the Let's Move program and cognitive function may be potentially or partially mediated by inflammatory biomarkers, BDNF and endothelial vascular function, we will first apply the standard regression-based approach in which several regression analyses are conducted and significance of the coefficients is examined at each step to evaluate the mediation effects. Furthermore, we plan to apply a cross-lagged panel model (CLPM) for longitudinal data to test the mediation effects of the biomarkers at T1 and T3 assessments. The CLPM is a multivariate model based on structural equation modeling (SEM) for testing mediational processes in longitudinal designs. Compared to cross-sectional mediation methods, the CLPM accounts for lagged effects in testing mediation hypotheses in longitudinal data, supports stronger inference about the direction of causation in comparison to models using cross-sectional data, and can reduce the probable parameter bias that arises when using cross-sectional data.

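### Aim 3 gives the baseline biomarker no place in the mediation models, so where exercise moves a marker, a pre-existing marker-cognition association can be declared mediation

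*Combined protocol and SAP*

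**What the plan says.** Section 4 sets a secondary aim: "To explore the potential mediation effects of inflammatory biomarkers, endothelial vascular function, and neuronal growth factor on the relationship between" the programme and cognition. Section 7 calls this Aim 3 and plans two analyses. The first is a standard regression approach in which "several regression analyses are conducted and significance of the coefficients is examined at each step to evaluate the mediation effects". The second is a cross-lagged panel model "to test the mediation effects of the biomarkers at T1 and T3 assessments", chosen partly because it "can reduce the probable parameter bias that arises when using cross-sectional data".

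The Aim 3 text gives no equation. It does not say whether the biomarker enters as a level or a change, at which visit the regressions take it, or with which covariates.

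Three other places bear on this:

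- Study Assessments: "Blood collection for the measures in Table 5 will occur at" baseline, T1, T2 and T3, so a pre-randomisation value of each marker exists.
- Section 7, Aim 1: "we calculate the z-score by adjusting the raw test score with the expected normal follow-up score", predicted from baseline characteristics. The analyses that follow use this z-score as the outcome.
- Section 7, general considerations: "Our analyses will account for potential confounding factors such as medications, gender, BMI and other specific confounders for each aim". Neither this list nor the Aim 1 model's list names the baseline biomarker.

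**The concern.** A mediation claim needs two links: arm to biomarker, and biomarker to cognition given arm. Randomisation protects the first. It does not protect the second, which compares people with different marker levels within an arm.

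The protocol expects such people to differ in cognition before any exercise. Table 5 describes sCD14 thus: "Marker of monocyte activation, is associated with neurocognitive impairment and HANDs and higher mortality in PLWH". It makes similar links for TNF-alpha and D-dimer, and the abstract does so for inflammatory markers generally. With no baseline marker in the model, the second link can be significant when changing the marker does nothing for cognition. Aim 2 hypothesises that exercise moves the markers, which supplies the first link.

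At stake is the trial's only question about mechanism. No efficacy conclusion depends on it.

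**Working it through.** **The plan's own figure.** Section 7 claims 80% power for a mediation effect of 0.39. It gives no metric, path values or test, so the figure can be neither reproduced nor refuted. Nothing below depends on it.

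**Inputs.**
- From the documents: 107 v 53 (section 5), two-sided tests at 0.05, and the cognitive z-score of Aim 1.
- Arm effect of 0.5 SD on both marker and cognition. This is assumed, but lies within the ranges section 7 cites (0.5 to 0.8, and 0.4 to 0.6).
- Not in the documents, so assumed: within-arm marker-cognition correlation r = 0.1 to 0.3; reliability R = 0.5 to 0.7 for both; no effect of marker on cognition; a stable-trait model, meaning two correlated permanent traits plus independent noise at each visit.

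**Mediator step.** The z-score is in effect Z = Y3 - R·Y0, where Y0 and Y3 are cognition at baseline and T3. Its within-arm variance is 1 - R². Its covariance with the T3 marker is r - R·r = r(1 - R). So

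k = corr(Z, T3 marker) = r·√((1 - R)/(1 + R)).

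With 160 participants and 157 residual degrees of freedom, the test statistic has mean δ = k·√157/√(1 - k²).

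**Arm steps.** 1/√(1/107 + 1/53) = 5.95.
- Arm to marker: 0.5 × 5.95 = 2.98, power 84.5%.
- Arm to Z: 0.5/√(1 - R²) × 5.95 = 4.17 (R = 0.7) or 3.44 (R = 0.5), power 98.6% or 93.0%.

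**Three-step rule** (all three coefficients significant), taken as the product of the three probabilities:

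| r | R | k | δ | mediator step | three-step |
|---|---|---|---|---|---|
| 0.1 | 0.7 | 0.042 | 0.53 | 8.2% | 6.9% |
| 0.1 | 0.5 | 0.058 | 0.72 | 11.2% | 8.8% |
| 0.2 | 0.7 | 0.084 | 1.06 | 18.4% | 15.4% |
| 0.2 | 0.5 | 0.115 | 1.46 | 30.8% | 24.2% |
| 0.3 | 0.7 | 0.126 | 1.59 | 35.7% | 29.7% |
| 0.3 | 0.5 | 0.173 | 2.20 | 59.6% | 46.9% |

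Simulation without the product approximation gives three-step rates of about 7-8%, 15-24% and 29-45% at r = 0.1, 0.2 and 0.3.

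**Lagged path, T1 marker to T3 cognition.** With z-scores at both visits, their within-arm correlation is q = R/(1 + R), which is 0.41 or 0.33. The partial correlation is k(1 - q)/√((1 - k²)(1 - q²)): 0.054 to 0.082 at r = 0.2, and 0.082 to 0.124 at r = 0.3. The path then rejects in 10-18% and 18-35% by formula, and in about 11-18% and 19-36% by simulation. Multiplying the simulated rates by the 84.5% chance that arm-to-marker is significant gives 9-15% and 16-30%.

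**If exercise does not move the marker.** The arm-to-marker step then passes only 5% of the time. Simulated false mediation is 0.6% (r = 0.2, R = 0.7) to 2.5% (r = 0.3, R = 0.5). With a 0.2 SD effect it is 3% to 12%.

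**If the association does not persist.** Suppose marker and cognition are correlated at baseline, then follow separate first-order autoregressive courses with coefficients a and b. Then cov(Y3, T3 marker) = r·a·b. The z-score subtracts b·Y0, whose covariance with the T3 marker is also r·a·b. The difference is zero, so there is no inflation. Simulation agrees (4-6%).

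**Remedies under the stable-trait model.**
- Biomarker as change from baseline: cov(Z, change) = r(1 - R) - r(1 - R) = 0, and the mediator step rejects at about 5%.
- Baseline biomarker and baseline cognition as covariates: the mediator step rejects in about 7-29% at r = 0.2 to 0.3. It is reduced but not removed, because one noisy baseline measures the trait imperfectly.

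**The case against.** The strongest reply is that the plan is silent rather than wrong. A reader might infer that it chooses to analyse biomarker level without baseline. The documents do not support that: the regressions have no covariate list at all, and the general confounder wording is open-ended and could take in a baseline marker. This stands. The defect is an omission, and it matters because the usual default, outcome on arm plus mediator, is the form exposed to the bias.

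A reader might also infer that a standing association by itself counts as mediation. It does not. Exercise must also shift the marker, and without that the three-step rule stays below 5%.

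Next, the plan has partial protection. The z-score removes part of the stable cognitive level, and the panel model is longitudinal and added with cross-sectional bias in mind. This also stands in part. Both reduce the problem, so it would be wrong to say that the lagged path carries the whole association. Neither uses the baseline marker, and the lagged path remains inflated under the stable-trait model. Rates computed on raw cognitive scores would be higher, but they do not describe this plan, because Aim 1 commits the later analyses to z-scores.

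Finally, every rate rests on an assumed model. Under the autoregressive alternative the inflation vanishes, and the documents do not show which applies. That limits what can be said about size. It does not remove the case for using a baseline already collected.

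**Conclusion.** The concern holds as a gap in specification with a real route to bias. Nothing in the plan places the baseline biomarker in the Aim 3 regressions or in the panel model, and randomisation does not cover the biomarker-to-cognition link.

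Under the stable-trait assumptions with 0.5 SD arm effects, false three-step mediation runs from slightly above nominal at correlation 0.1 to several times nominal at 0.3. These figures show direction and range; they do not predict this trial's error rate. Sample size matters less than the assumed correlation. In a separate simulation at reliability 0.7 and correlation 0.2 to 0.3, requiring only arm-to-marker and marker-to-cognition, the rate was 17-31% at 107 v 53 and 20-39% at 132 v 68, the other sample size in the documents.

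Priority is low to moderate: the aim is secondary and exploratory, but the correction is cheap.

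**What to change.** In section 7, Aim 3:

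- Adjust both the mediator and the outcome regressions for the participant's baseline biomarker, transformed as in Aim 2, and for baseline cognition.
- Include the baseline wave of biomarker and cognition in the cross-lagged model, so that the T1-to-T3 path is conditional on pre-exercise levels.
- Report the regressions with biomarker change from baseline as a sensitivity analysis.

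This takes two or three sentences and no new data.

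There are two costs. Baseline covariates leave some bias when a single baseline measurement is unreliable, as shown above, so a positive result should be read alongside the change form. The change form loses power at low reliability: with an assumed true path of 0.4, reliability 0.5 and 160 participants, joint significance was 65-67%, against 83-91% with baseline covariates. That trade-off is why the change form is proposed as a sensitivity analysis; the documents do not establish that it should lead.
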